28 JUN 2022

Version 5.0

Page: 34 of 149

Table 9–2 Schedule of PRO evaluations

Questionnaire	Baseline	Week 1 [§]	Week 2 [§]	Week 3 [§]	Week 4 [§]	Month 2**	Month 3 [‡]	Month 6 [‡]	Month 9 [‡]	Month 12 [‡]	Month 15 [‡]	Month 18 [‡]	Month 21 [‡]	Month 24 [‡]	Month 27 [‡]	Month 30 [‡]	Month 33 [‡]	Month 36 [‡]	Month 48	Month 60	Premature Discontinuation (Dropout)
PROMIS Scale v1.0 – Pain Intensity 3a ^{*†}	•	•	•	•	•	•	•	•	•	•	•	•	•	•	•	•	•	•	•	•	
PROMIS Scale v1.0 – Pain Interference 8a Participant Format ^{*†}	•	•	•	•	•	•	•	•	•	•	•	•	•	•	•	•	•	•	•	•	
Aberdeen Menorrhagia Severity Scale; and two intermenstrual bleeding questions	•						•	•	•	•	•	•	•	•	•	•	•	•	•	•	
SF-36	•							•		•				•				•		•	
Fibromyalgia Survey Questionnaire	•																				
Supplemental PRO Questionnaires										•				•				•	•	• ^{§§}	
Social Media Questionnaire																			• ^{§§}	•	

PRO=patient reported outcome, PROMIS=patient reported outcome measurement information system, SF-36=Short Form-36.

*All subjects are asked screening question “Did you experience pain in your pelvic area or in your lower abdomen during the past week?” Subjects that answer “Yes” complete both the PROMIS Scale v1.0 – Pain Intensity 3a and PROMIS Scale v1.0 – Pain Interference 8a Participant Format. Subjects that answer “No” do not have to complete the questionnaires.

[†] In the event a subject spontaneously reports an adverse event of pain, the subject will be given both the PROMIS Scale v1.0 – Pain Intensity 3a and PROMIS Scale v1.0 – Pain Interference 8a Participant Format questionnaires to complete at the time of reporting.

[§] Subjects completing ePRO questionnaires will receive email or text reminders to complete questionnaires 2 days prior to the scheduled completion date. The window for completion will be -2 days / +2 days for all questionnaires. If the questionnaire(s) are not completed by the scheduled completion date, another reminder will be sent and an alert will be sent to the site. Subjects completing paper questionnaires will not receive automated reminders and every effort will be made to ensure the subject completes the questionnaire within the window.

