### **3 Study design**

This study is a multicenter, open-label, non-randomized, continuous enrollment, prospective, observational postmarket surveillance study.

Study subjects will be women who are seeking permanent contraception and who have elected to undergo either hysteroscopic sterilization (Essure System ESS305) or laparoscopic tubal sterilization. Candidates who meet the inclusion and exclusion criteria, are willing to participate in the study, and are able to provide informed consent will be eligible for the study.

The sterilization procedure will proceed as it would if the subject were not in the trial. For subjects who elect to have hysteroscopic sterilization, 3 months following the placement procedure, the subject will be scheduled to return to the physician’s office or radiology facility for a confirmation test to evaluate Essure insert location and retention. Upon a satisfactory confirmation test, subject will be instructed to rely on Essure for contraception.

Follow-up contact will take place at 3 months ( $\pm 2$  weeks), 12 months ( $\pm 4$  weeks), 24 months ( $\pm 4$  weeks), 36 months ( $\pm 4$  weeks), 48 months ( $\pm 4$  weeks), and 60 months ( $-4$  weeks,  $+1$  week) post procedure. These visits will collect information that includes (but is not limited to) pelvic / lower abdominal pain, bleeding, gynecological procedures, AEs, and concomitant medication use.

Patient reported outcomes for pain (Patient Reported Outcomes Measurement Information System Scale V1.0, Pain Intensity 3a and Pain Interference 8a Participant Format) will be assessed at Baseline, Week 1, Week 2, Week 3, Week 4, Month 2, Month 3, and then every 3 months starting Month 6 until 36, if the response is “Yes” to the question “Did you experience pain in your pelvic area or in your lower abdomen during the past week?”

Patient reported outcomes for bleeding (Aberdeen Menorrhagia Severity Scale) will be assessed at baseline and then every 3 months starting Month 3 until Month 36.

Patient reported outcomes for health status (Medical Outcomes Study Short Form-36) will be assessed at Baseline, Month 6, Month 12, Month 24, Month 36, and Month 60.

Subjects will also complete a baseline questionnaire (Fibromyalgia Survey Questionnaire) that may help to identify women who are more likely to report pain events.

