### **4.2 General principles**

Statistical analyses will be explorative and descriptive in nature and no confirmatory hypothesis tests are intended to be performed; p-values will be interpreted as a metric for uncertainty. Therefore, no adjustment for multiplicity will be necessary.

All endpoints and variables will be analyzed by descriptive statistical methods. The number of data available and missing data, mean, standard deviation, minimum, lower and upper quartiles, median, and maximum will be calculated for continuous data. Frequency tables will be generated for categorical data. They will include the number of missing values as additional categories. Relative frequencies will be shown as percentages which will be calculated as a proportion including the category of missing values. The level of precision is defined in the table and figure shells with place holders for decimal places. Selected continuous variables will be categorized in a clinically meaningful way.

Unless specified otherwise, subjects in the analyses will be presented according to their initial index event.

The main analyses will be performed on the full analysis set as well as on a PS confounder-adjusted population of the full analysis set in order to adjust for measured confounding. Main analyses will also be performed in the full analysis set, adjusted full analysis set, reliance set, and adjusted reliance set. Details for derivation and adjustment are described in Sections 5.1 and 6.5.1.

The statistical evaluation will be performed using the software package SAS release 9.3 or higher (SAS Institute Inc., Cary, North Carolina, USA). Where propensity score design is conducted, SAS, the R package or STATA may be used.

All MedDRA terms or standardized MedDRA queries (SMQs) which are mentioned in this document are taken from the most updated MedDRA version. At the time of the analysis MedDRA concepts may have been changed; in this event, the validity of the terms and SMQs will be re-checked.

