#### **4.4.6 Other missing values**

Other missing values will not be imputed. Frequency tables for categorical data will include the number of missing values as additional categories. Percentages will be calculated as proportion of each category including the category of missing values.

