## 6.4 Outcome endpoints and variables

The main objective of this observational study is to evaluate under routine clinical practice conditions the incidence of important treatment-emergent AEs under hysteroscopic sterilization (Essure) and laparoscopic tubal sterilization. An AE is considered as treatment-emergent when it starts or worsens on or after the index date and up to the date of subject withdrawal or the censoring date, as described in Sections 4.3 and 6.1.3.

The outcome endpoint and variables are presented in Table 2. The descriptive analysis will be performed for all the variables listed below and the comparative analysis will be performed only for the main endpoints.

For the main endpoints, the subject incidence (regardless of the time each subject is “at risk”) is the number of subjects with treatment-emergent events divided by the number of subjects at risk.

Laboratory evaluation results will be compared to their normal ranges. Any values out of normal ranges will be identified. The change from baseline for each laboratory parameter will also be presented for each post-baseline visit.

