**Table 2 - Outcome endpoints and variables collected during treatment**

	Endpoint/Variable
Main Endpoints	
 
Subjects reporting AEs of chronic lower abdominal and/or pelvic pain after sterilization procedure
 
Subjects reporting AEs of abnormal uterine bleeding after sterilization procedure
 
Subjects with reported allergic/hypersensitive reactions
 
Subjects with newly diagnosed autoimmune disorders
 

	Endpoint/Variable
	
 
Subjects undergoing invasive gynecologic surgery (e.g., device removal or hysterectomy) after sterilization procedure (excluding second Essure placement attempts)
 

Patient Reported Outcomes	
 
MOS SF-36 (Version 2) which includes eight distinct health domains (physical function, role-physical, bodily pain, mental health, role-emotional, social functioning, vitality, and general health perceptions) and physical component summary and mental component summary scores
 
PROMIS Scale V1.0—Pain Intensity 3a, raw score, T-Scores, percentages of subjects who had T-Scores more than 50 and 60
 
PROMIS Scale V1.0—Pain Interference 8a, raw score, T-Scores, percentages of subjects who had T-Scores more than 50 and 60
 
AMSS and two intermenstrual bleeding questions used to characterize bleeding in subjects undergoing Essure placement and laparoscopic tubal sterilization, total raw scores and individual score for each question, percentage of subject having total scores greater than 40
 
FSQ: to investigate if scores on this instrument (continuous and categorical) correlate with chronic pelvic pain over the course of the study
 
Supplemental PRO Questionnaires
 
Social Media Questionnaire
 

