#### **6.4.6 Reporting of longitudinal data**

Analysis of longitudinal data (e.g., PRO data) will be descriptive.

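### PROMIS pain means will describe only women who screened positive for pelvic pain at that visit, and the SAP neither reports the screener nor separates a planned skip from a missed questionnaire

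*SAP*

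**What the plan says.** Protocol Table 9–2 puts the pain screener to every woman at each PROMIS time point. Those who answer No "do not have to complete the questionnaires". SAP section 3 repeats the gate: PROMIS is assessed at baseline, at the early time points "and then every 3 months starting Month 6 until 36, if the response is" Yes.

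For each PROMIS form, SAP Table 2 lists "raw score, T-Scores, percentages of subjects who had T-Scores more than 50 and 60". It does not list the screener, although Protocol 5.2.1 names the screener among the patient-reported outcome measures.

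Three general rules then apply:

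- Continuous data (SAP 4.2): "The number of data available and missing data, mean, standard deviation, minimum, lower and upper quartiles, median, and maximum will be calculated for continuous data".
- Absent values (SAP 4.4.6): "Other missing values will not be imputed". The imputation rules in 4.4.1 to 4.4.5 concern dates only.
- Categorical data (SAP 4.4.6): "Percentages will be calculated as proportion of each category including the category of missing values".

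Protocol 9.2.3.2 covers PROMIS scoring but assigns nothing to a No. On status, SAP 6.4.6 says "Analysis of longitudinal data (e.g., PRO data) will be descriptive", and SAP 6.4 says "the comparative analysis will be performed only for the main endpoints". SAP 6.6.2 makes the adjusted full analysis set primary for the questionnaires.

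**The concern.** A No is an answer, and the skip that follows is planned. Under the SAP's rules it looks the same as a questionnaire that was never returned. The mean at any visit is then an average over women with pelvic or lower abdominal pain at that visit. Who belongs to that group may depend on the procedure, so the balance obtained by matching at baseline is not guaranteed among the women actually averaged.

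If one procedure leaves more women with new mild pain, those women enter its average and pull it down. The arm can look better because more of its women hurt. Without the proportion answering Yes beside the mean, a reader cannot see this.

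A second rule adds to the problem. Protocol 5.2.1 has PROMIS given off-schedule when a woman spontaneously reports pain. SAP 4.6.3 fills a missing scheduled value from the closest associated unscheduled visit. A visit at which she truthfully answered No could therefore receive a score taken during a pain event.

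At stake is the description of pain intensity and interference that Protocol 5.2.1 promises for both groups.

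**Working it through.** **No plan figure to reproduce.** The documents give no expected Yes rate, PROMIS mean or PROMIS-based sample size. All rates and scores below are assumptions chosen to show the mechanism.

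**Formula.** Let p be the proportion answering Yes, m the mean score among them, and f the mean that No women would have had.

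- Planned arm mean = m
- All-responder mean = f + p(m − f)

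With the same f in both arms, arm 1 looks better in the planned table but is worse overall when m₁ < m₂ and p₁(m₁ − f) > p₂(m₂ − f).

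**Illustration A: T-scores.** Arm 1: p = 0.30, m = 54. Arm 2: p = 0.15, m = 57. The planned difference is 54 − 57 = −3.0.

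| f for No women | Arm 1 | Arm 2 | Difference |
|---|---|---|---|
| 35 | 40.7 | 38.3 | +2.4 |
| 40 | 44.2 | 42.55 | +1.65 |
| 45 | 47.7 | 46.8 | +0.9 |
| 50 | 51.2 | 51.05 | +0.15 |

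For example, at f = 40: 0.30 × 54 + 0.70 × 40 = 44.2, and 0.15 × 57 + 0.85 × 40 = 42.55. The difference is zero when 0.30(54 − f) = 0.15(57 − f), so 7.65 = 0.15f and f = 51. At f = 51 or above there is no reversal.

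**Illustration B: Interference 8a raw scores.** This form has eight items with five options. Protocol 9.2.3.4 gives the fourth option a rating of 4, so I infer coding 1 to 5 and a floor of 8. Set f = 8.

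- Laparoscopic: 20% Yes, mean 20, giving 8 + 0.20 × 12 = 10.4.
- Essure: 40% Yes, mean 18, giving 8 + 0.40 × 10 = 12.0.
- Planned difference: 18 − 20 = −2.0. All-responder difference: 12.0 − 10.4 = +1.6.

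With the laparoscopic values fixed, reversal needs an Essure mean below 20 and above 8 + 2.4/p. That bound is 17.6, 16.0, 14.0 and 12.8 at 25%, 30%, 40% and 50% Yes.

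**Illustration C: the mechanism.** Give Essure the same pain as the laparoscopic arm (20 per 100 women, mean 20), plus 10 per 100 women with mild pain (mean 13). The planned Essure mean is (20 × 20 + 10 × 13)/30 = 17.7, which looks better than 20. Nobody is better off. The all-responder difference is (30 × 17.67 + 70 × 8)/100 − 10.4 = +0.5.

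**When the sign does not reverse.** At equal Yes rates of 20% with means 18 and 20, the planned difference is −2.0 and the all-responder difference is 0.20 × (−2.0) = −0.4. In a simulation, latent pain was shifted uniformly by 0, 0.2 and 0.4 SD with a fixed cut-off for answering Yes. Conditional means rose from 16.8 to 17.4 to 18.1 and all-responder means from 9.75 to 10.44 to 11.32, so both moved the same way.

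**Percentages above a threshold.** Protocol 5.2.1 equates raw 22 on 8a with T = 60. Suppose 8 of 100 laparoscopic and 9 of 100 Essure women reach it, with 20 and 30 answering Yes. Among Yes women this is 8/20 = 40% v 9/30 = 30%. With all women in the denominator it is 8% v 9%. The SAP 4.4.6 rule gives the second pair, so the sign is safe, but No women and non-responders share one missing category.

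**The case against.** The strongest objection is that a No woman is not known to be free of pain. The screener (Protocol 17.1) asks only about the pelvic area and lower abdomen. The PROMIS items in Protocol 17.2 and 17.3 name no body site. Protocol 10.3 expects some women to have low back pain, chronic headache or fibromyalgia, and such a woman may answer No and still score above the floor. A reader might infer that every No should be scored at the instrument floor as the main analysis. The documents do not support that, and the floor T-score is not in them. This objection stands: Illustrations B and C rest on the floor assumption, and in Illustration A the reversal fades as f rises.

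Two other stronger readings also fail. A reader might infer that women with new-onset pain are lost from a planned change from baseline. SAP 6.4 and Table 2 specify change from baseline for laboratory measures, not for PROMIS. A reader might also infer that all the PROMIS outputs quoted are distorted in the same way. The threshold percentages are largely protected by the denominator rule.

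It is also fair to say that little rides on these tables. The pain endpoint is based on adverse events. No comparative PROMIS analysis is planned, and the counts of available and missing values would appear beside each mean. SF-36 bodily pain is collected from all women without a gate. Severity given pain, shown next to frequency of pain, is a legitimate description. That lowers the weight but does not remove the point, because the frequency is not listed in Table 2 and a missing count cannot separate No from non-response. The table shells mentioned in SAP 4.2 might settle some of this, but they are not part of the documents.

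**Conclusion.** The concern holds in a limited form. As written, scheduled PROMIS raw and T-score means describe only women with pelvic or lower abdominal pain at that visit, and planned skips are pooled with non-response. Such means can favour the arm with more women in mild pain. They do not have to: reversal needs a higher Yes rate together with a lower mean among those who answer Yes.

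The size cannot be fixed from the documents. Under the assumed T-score inputs, a planned difference of −3.0 becomes between +2.4 and +0.15 as the No mean runs from 35 to 50, and no reversal remains from 51. The effect is confined to descriptive, secondary output. It does not bias the adverse-event-based pain endpoint through these means. It is worth correcting because arm means shown side by side will be read as a comparison and the correction is cheap.

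**What to change.** Add to SAP Table 2 and section 6.4.6, with a cross-reference in 4.6.3:

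1. Report the proportion answering Yes by arm and visit, among women who answered the screener.
2. Code a No as a planned skip, separate from missing. Do not fill such a visit from an unscheduled pain-event score under the 4.6.3 rule.
3. Report the proportions with T-scores above 50 and 60 among all screener responders, counting a No as no pelvic-pain score above the threshold.
4. Label raw and T-score means as *among women reporting pelvic / lower abdominal pain*, and show them beside item 1.

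An all-responder summary with No set to the instrument floor may be added as a sensitivity analysis only, for the reason given above. Medians and proportions should accompany its means, because many values will sit at the floor.

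The cost is a few lines of SAP text, one derivation from data already collected, and a few extra table rows.

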- Potential new or worsening allergy / hypersensitivity symptoms (e.g., itch [pruritus], rash, hives [urticarial], facial edema, angioedema, allergy to metals, flushing, anaphylaxis), in addition to symptoms that could possibly be related to an inflammatory reaction (e.g., hair loss, fatigue, muscle pain, joint pain, joint swelling);
- Potential new or worsening autoimmune reactions;
- Intraoperative bleeding or complications after undergoing hysteroscopic sterilization with Essure or laparoscopic tubal sterilization, including additional surgical procedures to manage the complications;
- Chronic pelvic pain. Per the definition by the American College of Obstetricians and Gynecologists, chronic pelvic pain is pain in the pelvic area that lasts for 6 months or

longer. In those subjects reporting new or worsening lower abdominal / pelvic pain at any time during the study, either spontaneously or in response to the regularly scheduled PRO tool, evaluation of the event will note if duration of the pain meets this definition.

- Pregnancy (refer to Section 9.6.2);
- Upper genital tract infection (for example, endometritis, salpingo-oophoritis, salpingitis).

Allergic / hypersensitivity reactions

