#### **4.4.5 Main outcome events**

Incomplete start dates of outcome events for the time to event analyses will be imputed as follows:

- In case that only the day is missing, the date will be imputed as the first day of the month.
- In case that the day and the month are missing (i.e. only the year is available) the day and month will be imputed as January 1.
- In case the event start date is missing completely, index event date will be used as start date.
- If the imputed start date is before the index date, it will set to the index date.

Incomplete stop dates of outcome events for the time to event analyses will be imputed as follows:

- In case that only the day is missing, it will be imputed with last day of the month;
- In case that the day and the month are missing (i.e., only the year is available) it will be imputed as December 31.
- If the imputed dates are after the last date of contact, it will be set to the last date of contact.
- If the stop dates are completely missing, the event will be considered as ongoing at the time of end of study.

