Adverse Events	Any AE, Serious AEs, reason for serious AE, AE of special safety interest, AE intensity, AE related to study procedures or devices, type of procedure/device related to AE, AE outcome, pre-existing condition, concomitant medication, other non-study procedures
Contraceptive Method Post-procedure	Method used for contraception, duration of the contraceptive method used.
Concomitant Medication	Type of medication, main indication for medication
Additional Abdominal or Pelvic Surgery	Type of surgery performed, was surgery done for the purpose of sterilization/ re-sterilization , surgery due to an AE
Allergy/Hypersensitivity Evaluation, Autoimmune Disorder Evaluation, and PRO Alert Response	Symptom subjects reported, adjudication committee form, pathological findings, serum or plasma nickel and titanium levels, NiLPT and chromium LPT results, cytokine samples analysis , type of alert, pain alert response and bleeding response.
Study Completion	Did subject complete study, primary reason for premature discontinuation, time to premature discontinuation
Death	Number subjects died

a Only measured for Essure Group

b Only measured for laparoscopic tubal sterilization group

For the main outcomes, [Table 3](#) lists the SMQ search terms for abnormal uterine bleeding and lower abdominal and/or pelvic pain. Per the definition by the American College of Obstetricians and Gynecologists, chronic pelvic pain is pain in the pelvic area that lasts for 6 months or longer (i.e., the stop date of the pain minus start date is longer than 182 days, or by the time of EOS, the subject still has pain ongoing with start date 182 days before EOS).

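### Chronic pain is classified by subtracting AE dates, and the SAP does not keep imputed or assumed-ongoing dates out of that test, so some short pain with missing dates would count as chronic

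*SAP*

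**What the plan says.** SAP Table 2 lists "Subjects reporting AEs of chronic lower abdominal and/or pelvic pain after sterilization procedure" first among the main endpoints. The text after that table takes the clinical definition ("chronic pelvic pain is pain in the pelvic area that lasts for 6 months or longer") and turns it into date arithmetic with two limbs: "the stop date of the pain minus start date is longer than 182 days", or, at EOS, "the subject still has pain ongoing with start date 182 days before EOS".

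SAP 4.4.5 sets the date rules for main outcome events.
- **Start date:** the first of the month if the day is missing, 1 January if only the year is known. For a wholly missing start, "In case the event start date is missing completely, index event date will be used as start date". No imputed start may precede the index date.
- **Stop date:** the end of the month if the day is missing. If only the year is known, "it will be imputed as December 31". No imputed stop may exceed the last contact. For a wholly missing stop, "If the stop dates are completely missing, the event will be considered as ongoing at the time of end of study".

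SAP 4.4.2 gives the same stop-date rules for AEs in general.

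The protocol provides a second source. For new or worsening pelvic pain, section 9.6.1.1 says that "evaluation of the event will note if duration of the pain meets this definition", and section 5.2.1 likewise says it will be determined whether the duration qualifies. Protocol 9.6.1.2.5 also records an outcome for every AE, including resolved. The SAP definition uses neither. SAP 6.8 plans one sensitivity analysis, which ignores censoring events and leaves dates as they are.

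**The concern.** Each imputation rule can only lengthen an AE or leave its length unchanged. That matters little where a date is used only to time an event. Here the two dates are subtracted to decide whether the event exists, so missing information can turn non-chronic pain into a main-endpoint event but can never do the reverse.

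The pain search list in SAP Table 3 admits terms that are often short or cyclic, such as incision site pain, ovulation pain and dysmenorrhoea. Duration is the filter that separates these from chronic pain, and it is the filter that missing dates weaken. An AE recorded as resolved but without a stop date would be carried as ongoing to EOS.

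At stake is the chronic-pain proportion in each arm and, if date completeness or acute pain differs between arms, the contrast between them. Nothing in the plan would show how many chronic events depend on assumed dates.

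**Working it through.** **1. The cut-off.** 26 weeks x 7 = 182 days, and 6 x 365.25/12 = 182.6 days. Six calendar months span 181 to 184 days. The 182-day figure is a fair rendering of six months and is not in dispute.

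**2. One short AE under each pattern.** Take index date 15 March 2018, EOS 15 March 2023 (five years) and true pain from 10 to 13 June 2019, which is 3 days. Apply the SAP 4.4.5 rules:

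| What is missing | Dates used | Days | Class |
|---|---|---|---|
| nothing | 10 Jun-13 Jun 2019 | 3 | not chronic |
| stop | 10 Jun 2019-EOS | 1,374 | chronic |
| start | index-13 Jun 2019 | 455 | chronic |
| day and month, both dates | 1 Jan-31 Dec 2019 | 364 | chronic |
| day and month, stop only | 10 Jun-31 Dec 2019 | 204 | chronic |
| day and month, start only | 1 Jan-13 Jun 2019 | 163 | not chronic |
| day only, both dates | 1 Jun-30 Jun 2019 | 29 | not chronic |

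**3. Where the rules stop short.**
- Known start, year-only stop: 1 July to 31 December is 183 days and 2 July to 31 December is 182. Only onsets on or before 1 July cross the cut-off.
- Year-only start, known stop in a later year than the index: the stop must be on or after 3 July (2 July in a leap year).
- Both dates year-only, in the index year: the floor applies. With index 15 July, 15 July to 31 December is 169 days, not chronic. Any index date from 2 July onward gives at most 182 days.
- Missing start: duration runs from index, so pain that stops within 182 days of the procedure stays non-chronic.
- Day missing on both dates: at most 30 days are added at each end, 60 in all, so true duration must be at least 183 - 60 = 123 days. Example: 31 March to 1 August is 123 days and becomes 1 March to 31 August, 183 days.

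**4. How often each pattern converts non-chronic pain.** Assumptions: index dates spread over about 19 months, onset uniform over five years, no dropout, 20,000 simulated AEs per pattern. Share classed chronic:

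| Pattern | True 3 days | True 150 days |
|---|---|---|
| complete dates | 0% | 0% |
| day missing, both | 0% | 30% |
| year-only, one date | 46% | 89% |
| year-only, both | 95% | over 99% |
| stop missing | 90% | 98% |
| start missing | 90% | 98% |
| both missing | 100% | 100% |

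The missing-stop figure can be checked by hand: (1,826 - 182)/(1,826 - 3) = 1,644/1,823 = 0.90. If onsets cluster soon after the procedure, the missing-stop share rises and the missing-start share falls.

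**5. Illustrative effect on the endpoint, missing stop dates only.** Added proportion = (women with non-chronic pain) x (share of those lacking a stop date) x 0.90.
- Low: 0.20 x 0.01 x 0.90 = 0.0018, about 0.2 points.
- High: 0.40 x 0.10 x 0.90 = 0.036, or 3.6 points.

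The first two factors are assumptions. The documents give no rate of incomplete AE dates and no pain incidence.

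**The case against.** The strongest counter-argument is scope. SAP 4.4.5 says its rules are for time-to-event analyses, and 6.4 never says that imputed dates feed the chronicity test. This stands in part, mainly for start dates. For stop dates, 4.4.2 covers AEs generally. Time to first event needs no stop date, and chronic pain is the only main endpoint whose definition uses one, so chronicity is the evident use of the stop-date rules in 4.4.5. At the least, the SAP leaves the question open.

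A reader might infer that every incomplete date makes pain chronic, or that year-only dates always yield 364 days. The documents do not support this. The index-date floor and last-contact cap block some year-only cases, including index-year cases where much post-procedure pain would fall, and a missing day cannot make short pain chronic.

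Two further points stand. The electronic data capture system has completeness checks and site queries (Protocol 12.1), and consistency checks are left to a Data Management Plan outside these documents, so few blank or year-only dates may survive to lock. The rules are also the same in both arms, and the analysis is declared exploratory. That limits the weight of the point but does not remove it, because a descriptive proportion is still inflated and nothing planned would reveal it.

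**Conclusion.** The concern holds in a bounded form. Followed as written, the SAP lets a missing stop date, and often a missing start or year-only dates, decide that non-chronic pain is chronic. The direction is known: over-counting in both arms. The start-date half rests on reading 4.4.5 as applying to the classification; the missing-stop half does not need that reading.

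The size cannot be established. The range of 0.2 to 3.6 points depends on the assumed rates in step 5 and on onsets spread evenly over five years.

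A reader might also infer that the comparison between arms is biased. That follows only if date completeness or acute pain differs by arm. The protocol does expect that some AEs may be reported more in one group (section 5.2.1), and incision pain plausibly belongs to laparoscopy, but neither shows that dates are less complete in one arm. This merits a change to the SAP before database lock; it does not invalidate the endpoint.

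**What to change.** 1. In SAP 6.4, state that neither an imputed date nor the assumption that an AE without a stop date is ongoing can by itself make pain chronic. Both need naming, because 4.4.2 says that a wholly missing stop date is not imputed.
2. Where missing or incomplete dates leave the duration unsettled, use the case-level chronicity determination that the protocol requires, together with the AE outcome. An AE recorded as resolved is not treated as ongoing. Query the site before lock if the determination is blank. The documents do not show an eCRF field for it, so its availability should be checked first.
3. Add to SAP 6.8 a sensitivity analysis that counts only AEs whose known dates establish more than 182 days.
4. Report by arm the number of chronic events that depend on imputed or assumed-ongoing dates, with shortest-duration and longest-duration bounds.
5. Keep the earliest-start rule for event timing.

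Mid-points between visits are not a safe substitute. After Month 36 the pain screener is scheduled only at Months 48 and 60 (Protocol Table 9-2). One positive answer at Month 48 between negatives at 36 and 60 would give mid-points at Months 42 and 54, a duration of 12 months, and would recreate the error.

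The cost is SAP wording, a few targeted queries before lock, and a few extra runs.
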